8.1.2.1 Hypothesis

Let P be the proportion of LUX-Dx monitored Treatment Subjects with Treatment Success through the Day 360 Assessment and PG be the performance goal, the following hypothesis will be tested in a one-sided test at 0.025 significance level.

$H_0: P \leq PG$

$H_A: P > PG$

Where $PG = 40\%$.

8.1.2.2 Sample Size

The sample size estimate was obtained using the binomial exact method. The following assumptions were used:

Table 8.1-3: Assumptions for the Primary Effectiveness Endpoint Sample Size Estimate

Assumptions	Primary Effectiveness Endpoint
Expected rate	55%
Performance goal	40%
Attrition (per year)	10%
Significance level (one-sided)	0.025
Power	90%
Evaluable patients	122
Patients accounting for attrition	136

Under the methods and assumptions outlined above, the required sample size for this endpoint after attrition is 122; therefore, approximately 136 LUX-Dx monitored Treatment Subjects are required for the analysis of the primary effectiveness endpoint.

8.1.2.3 Statistical Methods

The proportion of LUX-Dx monitored Treatment Subjects with PersAF Treatment Success through the Day 360 Assessment will be estimated using the Kaplan Meier method. The 97.5% one-sided lower confidence limit of the observed Treatment Success rate will be compared to the performance goal of 40%. If the lower confidence limit is greater than the performance goal, the null hypothesis will be rejected. The confidence limit will be calculated as the pointwise confidence limit using log-log methodology.

Each LUX-Dx monitored Treatment subject will be classified as Treatment Success (event-free) or Treatment Failure (PEE event). Subjects must have an active LUX-Dx device with established LATITUDE Clarity connection by the end of the effectiveness evaluation period to be included in PEE analysis. Subjects who withdraw or die from the study prior to the Day 360 Assessment, without experiencing a PEE event, will be censored on the date of withdrawal or death. Subjects who are determined to be Severe COVID-19 Subjects during trial participation without experiencing a PEE event will be censored as of the Onset Date of the condition.

LUX-Dx data will be used to simulate intermittent arrhythmia monitoring methods consistent with the methods used in ADVANTAGE AF Phase 1. Bi-monthly (asymptomatic) event monitor transmissions will be simulated by randomly selecting LUX-Dx data from two, 2-minute time windows every 30 days starting on the date of the Day 90 assessment. Each 30-day interval contains 2,592,000 seconds from which 2 seconds will be selected via simple random sampling and used as the starting point for a 2-minute (120 second) window. The first 2-minute window will be removed prior to sampling the second 2-minute window to avoid overlapping windows. The sampling seed will equal the date of the first subject enrollment..

Only 2-minute windows occurring after the blanking period will be used for analysis. Thirty-day intervals will repeat until an interval contains an in-window Day 360 Assessment, Day 390, or subjects' End of Study date, whichever occurs first. In the final 30-day interval, only 2-minute windows occurring on or prior to the in-window Day 360 Assessment, Day 390, or subjects' End of Study date, will be used for analysis. If a 2-minute window occurs on the same day as a scheduled study visit (Day 180 or Day 360 Assessment) or on the same day as the simulated Holter patch, then a new 2-minute window will be randomly selected to avoid overlapping with the 12-lead ECG recording and simulated Holter patch recording.

Twenty-four (24) hour Holter patches will be simulated by selecting LUX-Dx data from the day before the Day 180 and Day 360 Assessments. The day before was selected to avoid overlapping with the 12-Lead ECG recordings from each visit. For subjects that had a missed visit for the Day 180 or Day 360 assessment, the last day of the subject's visit window will be used for the simulated Holter patch.

Recurrence will be defined as a stored LUX-Dx AT or AF episode that is adjudicated as containing at least 30 seconds of atrial arrhythmia and that overlaps a simulated window by any amount. Additionally, all LUX-Dx recorded symptomatic episodes and all 12-lead ECGs will be assessed for AF, AFL, or AT recurrence as defined in Protocol Section 23.2.

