2.3 Non-Investigational Devices

2.3.1 LUX-Dx Insertable Cardiac Monitor

The LUX-Dx ICM is a small, leadless electronic device implanted under the skin in the left anterior chest wall. Its primary functions are to monitor, record, and store data related to cardiac arrhythmias. Two electrodes on the body of the device are used to monitor and record the patient's subcutaneous ECG (S-ECG) data when specific arrhythmias (according to the device-programmed settings) are detected, which include pause, bradycardia, tachycardia, AF, and atrial tachyarrhythmias (AT). In addition, the device will record S-ECG data when the patient triggers the device to record via the myLUX patient app. The ICM's memory can store up to 60 minutes of S-ECG recordings. Initial default arrhythmia detection parameters are provided by LATITUDE Clarity according to the Reason for Monitoring.

Figure 2-5: LUX-Dx ICM Device and Mobile App

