8.3.3.7 Sensitivity of Effectiveness to LUX-Dx S-ECG Storage

The impact of the LUX-Dx S-ECG storage capacity on the determination of Detectable AF, AFL, and AT will be assessed for the PEE. LUX-Dx detected AT and AF episodes or patient-triggered symptomatic episodes without a stored S-ECG will be considered to have confirmed AF, AFL, or AT and included in the determination of Detectable AF, AFL, and AT.

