Inclusion Criteria:

1. Subjects enrolled in Phase 2 of the ADVANTAGE AF study with an active LUX-Dx ICM device.

Exclusion Criteria:

None

Sub-Study Procedures

No additional study procedures or follow-up assessments are required for subjects that agree to participate in the LUX-Dx sub-study. The LUX-Dx ICM device will continue to be programmed as defined within the ADVANTAGE AF Phase 2 protocol or as determined most appropriate to assess the subjects' heart condition per physician assessment. Subjects will continue to use their myLUX patient application to complete manual transmissions when experiencing symptoms and remain connected to the LATITUDE Clarity™ system throughout the duration of the trial.

Data Collection and Analysis

Once a LUX-Dx subject completes their Day 360 assessment, they will continue to be remotely monitored via LATITUDE Clarity for up to a total of 3 years (36 months) from the ADVANTAGE AF index ablation procedure. There is no additional data collection that will need to be entered in the study database after the Day 360 assessment.

Subjects will need to maintain connection between their device and the myLUX patient app to ensure continuous arrhythmia monitoring. It is recommended that subjects do not stay disconnected for more than two (2) weeks to ensure no data is overwritten.

No additional study procedures or follow-up assessments are required for subjects that agree to participate in the LUX-Dx sub-study, however, participating subject's electronic medical records or health care claims may be reviewed to assess for clinical events associated with ablation efficacy (e.g., cardioversions, re-ablations, hospitalizations).

Adverse events will not be reported through the clinical study database after the subject completes their active participation (i.e., Day 360 assessment visit) in Phase 2 of the

ADVANTAGE AF Study. Adverse events will be reported through normal commercial channels/complaint processes as applicable by sites.

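### Phase 2 effectiveness analysis has no rule for simulated monitoring windows without retrievable LUX-Dx data, so that time counts as event-free and can only favour success

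*Combined protocol and SAP*

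**What the plan says.** All references are to Appendix A (Phase 2) unless stated.

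- **Entry to the analysis.** Section 8.1.2.3: "Subjects must have an active LUX-Dx device with established LATITUDE Clarity connection by the end of the effectiveness evaluation period". Section 8.2.1 repeats this and leaves out only subjects with no device or no connection by that point.
- **Windows.** Section 8.1.2.3 draws two 2-minute windows per 30 days from the Day 90 Assessment, plus a simulated Holter day before the Day 180 and Day 360 Assessments. A 2-minute window that falls on one of those visit days or on a simulated Holter day is redrawn. Nothing is said about windows without data.
- **Event.** Recurrence in a window requires a stored LUX-Dx episode, adjudicated to contain at least 30 seconds of atrial arrhythmia. Symptomatic recordings and 12-lead ECGs also count.
- **Censoring.** Only withdrawal, death and Severe COVID-19.
- **Device memory.** Section 2.3.1: "The ICM's memory can store up to 60 minutes of S-ECG recordings". Appendix B, on follow-up after Day 360: "It is recommended that subjects do not stay disconnected for more than two (2) weeks to ensure no data is overwritten".
- **Sensitivity analyses.** Section 8.3.3.1 covers subjects who leave the study. Section 8.3.3.7 covers detected or patient-triggered episodes, which "without a stored S-ECG will be considered to have confirmed AF, AFL, or AT".

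**The concern.** A subject can be in the primary analysis with part of Days 91-360 not covered by any recoverable recording. The windows are drawn over that part all the same. No stored episode means no event, and no censoring rule applies, so absence of data is scored the same way as absence of arrhythmia.

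The source of the problem is lost or absent recordings. Late connection matters only as one way in which recordings may be lost. What is at stake is a one-directional error in a single-arm comparison with a fixed 40% goal, where Section 8.2.3 claims an overall type I error of no more than 2.5%.

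**Working it through.** **1. The plan's own figure.** Inputs from Sections 8.1.2.1 and 8.1.2.2: one-sided 0.025, goal 40%, expected rate 55%, power 90%, attrition 10% per year, exact binomial. The smallest n with at least 90% power is 121. At n = 122 the rule is 60 or more successes, with exact alpha 0.0248 and power 91.6%. Then 122/0.9 = 135.6, which rounds up to 136. The stated 122 and 136 reproduce. At n = 258 (planned enrolment, set by the safety endpoint) the rule is 120 or more successes, with alpha 0.0197.

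**2. What missing time does to coverage.** Day 90 to Day 360 is 270 days, or nine 30-day intervals, so 18 two-minute windows and 2 Holter days. If nothing before Day 180 can be retrieved, about 12 of 18 windows and 1 of 2 Holter days are covered. If nothing before Day 300 can be retrieved, about 4 of 18 and 1 of 2. Both subjects satisfy the entry rule.

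**3. Effect on the success rate.** Assumptions, none of them in the documents:
- f = share of analysed subjects with missing recordings
- h = share of Days 91-360 missing for them
- q = share of failures that only the LUX-Dx would show, taken as 0.7
- constant failure rate over the period

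With true success S, the apparent success of an affected subject is S^(1 − q·h), and the overall rise is f × [S^(1 − q·h) − S].

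At S = 0.55 and h = 0.5: 0.55^0.65 = 0.678, a difference of 0.128.
- f = 0.05: 0.64 points
- f = 0.10: 1.28 points

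With f = 0.10 and h = 0.9: 0.55^0.37 = 0.802, a rise of 2.52 points. Over q = 0.5-0.9, f = 5-20% and h = 25-90%, the rise runs from 0.2 to 6.9 points.

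**4. Effect on type I error.** At S = 0.40 and h = 0.5: 0.40^0.65 = 0.551, a difference of 0.151. The exact binomial rule from step 1 is applied at the inflated rate. The planned test is a Kaplan-Meier limit, so these values are approximate.

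| f | Rise (points) | n = 122 (nominal 0.025) | n = 258 (nominal 0.020) |
|---|---|---|---|
| 5% | 0.8 | 0.037 | 0.035 |
| 10% | 1.5 | 0.053 | 0.059 |

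**5. Distance from the decision at the expected rate.** 55% of 258 is about 142 successes. The rule needs 120, so 142 − 119 = 23 successes would have to become failures to lose the test. A rise of 0.64 to 1.28 points is 258 × 0.0064 to 258 × 0.0128, about 2 to 3 subjects.

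**The case against.** A reader might infer that every subject connected late is credited as arrhythmia-free up to the connection date. The documents do not support that. Insertion is required within 7 days of the procedure (Section 7.6), and the device detects and stores on its own (Section 2.3.1). Episodes stored before connection may still be retrieved. The 60-minute limit concerns S-ECG. The Appendix B warning speaks of data and does not say whether the detection log is lost too.

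Other points on the plan's side:
- **Safeguards.** LATITUDE enrolment takes place before, during or immediately after insertion. Subjects disconnected for more than 7 days should be contacted (Section 7.6). Sites check transmissions at every visit from Day 7, where available, to Day 360 (Sections 7.9 to 7.13). Many subjects with long gaps are therefore unlikely. None of these steps is an analysis rule.
- **Existing analyses.** Section 8.3.3.6 turns successes into failures one by one because of the 4-hour AT setting. Its tipping count does not depend on why an event was missed, so it can be set against the number of poorly covered subjects. Section 8.3.3.7 handles detections without an S-ECG. Together they partly bound the effect, but neither identifies subjects or time without data.
- **Later detection.** The model in the working lets a failure vanish if it is unrecorded when it occurs. Recurrent arrhythmia can still be caught by later windows, the Day 360 Holter day, ECGs or symptomatic recordings, so the model tends to overstate.
- **Phase 1 parallel.** Phase 1 Section 8.1.2.3 does not censor for missed transmissions either, under the same 55% and 40%. That helps comparability with Phase 1, but it does not turn missing data into evidence of success.
- **Separate SAP.** Section 11.2 leaves the formal adjudication process to the Phase 2 SAP, and other details are deferred there too. That text is not in these documents, so a rule may exist that cannot be seen here.

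**Conclusion.** The point stands in limited form. Followed as written, Sections 8.1.2.3 and 8.2.1 admit subjects with incomplete LUX-Dx data, and time without retrievable data counts towards success. This follows from the entry, event and censoring rules taken together. No single sentence says that such windows are negative.

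The direction is certain, but the size is not. The documents give neither the number of affected subjects nor the share of failures that only the LUX-Dx would show. Under the assumed 5-10% of subjects, half the period and 70%, the rise is about 0.6-1.3 points at 55%. Type I error at the goal moves to about 0.04-0.05 (n = 122) or 0.035-0.059 (n = 258). The true effect is probably smaller, given the safeguards and later detection.

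A reader might conclude that the trial's result is at risk. The documents do not support that: if success is near the expected 55%, a shift of 2 to 3 subjects is far from the roughly 23 needed at n = 258. The gap would matter if the observed rate fell close to the decision limit.

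**What to change.** **In Section 8.1.2.3:**
- Extend the existing redraw rule. A 2-minute window or Holter day that falls in time without retrievable LUX-Dx data is redrawn from recorded time in the same 30-day interval or visit window.
- Where no recorded time exists there, mark the window or day as missing, not negative.
- Report coverage for each subject.

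**In Section 8.3.3, add:**
- The primary effectiveness analysis restricted to subjects with retrievable recordings from the Day 90 Assessment, with all failure types counted for them.
- A tipping-point analysis that turns successes with uncovered intervals into failures.

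If the separate SAP already has such rules, Section 8.1.2.3 should cite them.

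Delayed entry into the risk set at first recording is not recommended if failures that need no LUX-Dx still count from Day 0. A poorly covered subject cardioverted at Day 120 would count as a failure, while an event-free one would add no earlier risk time. Entry would then depend on outcome and bias success downwards.

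**Cost:** SAP wording, some added analysis of device data, and possibly a slightly lower success rate. The sample size of 122 (136 with attrition) does not change.

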8.3.6 Treatment Success Rate by Arrhythmia Detection Method

PersAF Treatment Success rates through Day 360 Assessment will be compared between ADVANTAGE AF Phase 1 and Phase 2 Treatment Subjects to assess differences in chronic success when using the continuous monitoring from an ICM to simulate non-continuous monitoring for recurrence compared to standard assessment based on true Holter monitoring and periodic

transmissions from event monitors. A propensity score analysis utilizing inverse probability of treatment weights (IPTW) will be used to estimate the absolute difference in PersAF Treatment Success rates between detection groups (ICM vs. Standard) while minimizing the effects of confounding variables. Details of this analysis will be included in the Appendix A of the ADVANTAGE AF SAP.

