Atrial arrhythmia episodes (asymptomatic and symptomatic) captured by the LUX-Dx ICM will be analyzed by BeatLogic Core Lab Adjudicator Tool for atrial arrhythmia rhythm determination, including episodes captured by LUX-Dx during the pre-defined time periods for the Primary Effectiveness Endpoint. Specified arrhythmic events recorded by LUX-Dx ICM may additionally be analyzed by independent experts for rhythm determination. The ADVANTAGE AF Phase 2 Statistical Analysis Plan will define the formal process for adjudication of recurrence episodes collected by LUX-Dx for the study for endpoint analyses.

11.3 *Cardiac Imaging Core Laboratory*

A qualified CICL will be established to receive, review, and assess any cardiac MRIs and CTs obtained for the evaluation of potential PV stenosis.

Baseline cardiac MRIs and CTs will only be read by the CICL if subsequent events result in follow-up imaging for the assessment of potential PV stenosis.

Pulmonary Vein Dimensions

Treated veins to be assessed will have the baseline and post-ablation assessments of standardized diameters (See definition of PV Diameter in **Section 23.2**).

Cardiac Imaging Data Review and Transmission

The CICL will analyze PV dimensions, calculate changes in dimensions, make available the primary data for review and transmit the PV dimensional analyses of each imaging study to the Sponsor for inclusion in the study dataset.

12 Deviations

Deviation requirements remain the same as Phase 1 of the ADVANTAGE AF study and can be found in **Section 12** of the Phase 1 clinical investigational plan.

13 Device Accountability

13.1 *Investigationally Labeled Test Devices*

Table 13.1-1 below shows a list of FARAPULSE PFA System components for which device accountability is required by the investigational site.

Table 13.1-1 : Device Accountability for the FARAPULSE PFA System

Component	Subcomponents
FARAWAVE PFA Catheter	1. FARAWAVE Pulsed Field Ablation Catheters (31mm and 35mm) 2. FARASTAR Catheter Connection Cable
FARAPPOINT PFA Catheter	1. FARAPPOINT Pulsed Field Ablation Catheters
FARASTAR PFA Generator and Related Equipment	1. FARASTAR Pulsed Field Ablation Generator 2. FARASTAR Recording System Module 3. FARASTAR Mapping System Module
FARADRIVE Steerable Sheath	FARADRIVE Steerable Sheath

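### Does drawing the simulated event-monitor windows from a single seed leave the Phase 2 effectiveness result hanging on an arbitrary date?

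*Combined protocol and SAP*

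**What the plan says.** Appendix A 8.1.2.3 rebuilds Phase 1's intermittent monitoring from the continuous LUX-Dx record. Two windows are drawn in each 30-day interval from the Day 90 Assessment onward: "2 seconds will be selected via simple random sampling and used as the starting point for a 2-minute (120 second) window". The draw is reproducible by rule: "The sampling seed will equal the date of the first subject enrollment". A window that lands on a scheduled visit day or a simulated Holter day is replaced.

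The event is then defined: "Recurrence will be defined as a stored LUX-Dx AT or AF episode that is adjudicated as containing at least 30 seconds of atrial arrhythmia", and any overlap with a simulated window is enough. The other routes to failure involve no random draw. The simulated Holter days are fixed as the day before the Day 180 and Day 360 visits, and "all LUX-Dx recorded symptomatic episodes and all 12-lead ECGs will be assessed for AF, AFL, or AT recurrence". Acute procedural failure, re-ablation, cardioversion and disallowed drug use also count, by the definitions in 3.4.

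Section 8.3.3 lists seven sensitivity analyses: missing data, other left atrial ablation, amiodarone, timing of drug discontinuation, a late Day 360 visit, AT/AFL detection, and S-ECG storage. None varies the draw. Sections 8.3.3.5, 8.3.3.6, 8.3.6 and 11.2 leave some endpoint detail to a SAP whose text is not part of the document reviewed.

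**The concern.** For a subject with short or infrequent asymptomatic episodes, success or failure can depend on which seconds the generator picks. Another seed would classify some subjects differently, and at the pass boundary one subject decides the test. The sponsor evidently cares about such features of the monitoring, since it tests neighbouring ones: "The impact of the LUX-Dx S-ECG storage capacity on the determination of Detectable AF, AFL, and AT will be assessed for the PEE", and 8.3.3.6 tests the AT/AFL setting. The draw is the one element of detection that is random by construction and has no matching analysis in 8.3.3. If the result fell near the boundary, a pass or a fail might owe something to the seed, and no pre-specified table would show by how much.

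**Working it through.** **1. The plan's own figure.** Appendix A, Table 8.1-3: 55% expected, 40% performance goal, one-sided 0.025, 90% power, 122 evaluable, 136 enrolled. By the exact binomial, the smallest count r with P(X ≥ r | 122, 0.40) ≤ 0.025 is r = 60. This gives alpha 0.0248 and power 91.6% at 55%. Attrition: 122 / 0.90 = 135.6, so 136. The figure reproduces.

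**2. The pass boundary at the planned enrolment of 258.** With no censoring, s = x/n and se = √[(1−s)/(ns)], the log-log lower limit is exp(−exp(log(−log s) + 1.96·se/|log s|)).

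| Successes / n | Rate | Lower limit | Result |
|---|---|---|---|
| 119 / 258 | 46.1% | 39.95% | fail |
| 120 / 258 | 46.5% | 40.3% | pass |
| 142 / 258 | 55.0% | 48.8% | pass |

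Allowing 10% attrition (n = 232), the boundary is 108 successes (46.6%, limit 40.02%). The rule of 120 or more out of 258 has exact alpha 0.0197 at 40% and power 99.7% at 55%.

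**3. Why the draw is neither bias nor uncounted noise.** Let p_i be the chance, over draws, that subject i fails, given that subject's own record. After one draw the outcome is a single yes/no variable. Across subjects and draws together its mean is the average failure rate π and its variance is π(1−π). With hits independent between subjects, the variance of the observed rate is π(1−π)/n. The between-draw part, Σp_i(1−p_i)/n², is a component of that total, not an addition to it. The planned interval therefore already covers it.

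**4. Size of the between-draw part.** Windows: (360 − 90)/30 × 2 = 18. A Day 90 visit on Day 104 with a Day 360 visit on Day 330 gives about 15, and follow-up from Day 90 to Day 390 gives 20. The documents give neither burden nor episode length, so the following are assumptions: 60-minute episodes, burden b of 0.1% to 5%, and 5% to 30% of 258 subjects whose outcome depends on the windows alone. A 2-minute window touches an episode with probability q = b × 62/60. The chance of at least one hit is p = 1 − (1−q)^18:

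- b = 0.1%: p = 1.8%
- b = 1%: p = 17%
- b = 5%: p = 62%

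With m window-dependent subjects the SD across seeds is √[m·p(1−p)]/258:

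| Share dependent (m) | b = 0.1% | b = 1% | b = 5% |
|---|---|---|---|
| 5% (13) | 0.19 pts | 0.53 pts | 0.68 pts |
| 20% (52) | 0.38 pts | 1.05 pts | 1.36 pts |
| 30% (77) | 0.46 pts | 1.28 pts | 1.65 pts |

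The sampling standard error at the boundary is √(0.465 × 0.535/258) = 3.1 points. A second model, also on assumed inputs (burden spread over 0.1–10%, 1- to 24-hour episodes, both Holter days counted, 10–40% of subjects affected), gives 0.4 to 1.3 points.

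**5. Effect on the verdict.** Take m = 52 and b = 1%, with hits binomial(52, 0.171). The share of seeds that pass, by the mean number of successes over all draws, is:

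| Mean successes | Rate | Seeds that pass |
|---|---|---|
| 118 | 45.7% | 32% |
| 120 | 46.5% | 61% |
| 122 | 47.3% | 84% |
| 124 | 48.1% | 95% |
| 128 | 49.6% | 99.8% |
| 142 | 55.0% | essentially all |

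Under the harshest inputs in the first table (m = 77, b = 5%) the shares at 124 and 128 are 83% and 97%.

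**6. What the plan already offers near the boundary.** One to two points is 0.01 × 258 to 0.02 × 258, or about 3 to 5 subjects. Section 8.3.3.6 turns successes into failures one at a time until the endpoint fails. Its purpose is AT/AFL detection, but for a passing result that count is the margin in subjects. Section 8.2.2 undertakes to provide the full dataset so that others can assess error and bias themselves. With the window algorithm stated in 8.1.2.3, a redraw needs nothing further except the stored episodes and their classifications.

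**The case for a change.** The best argument for a change is that it costs almost nothing. In Phase 1 a transmission happened once and could not be repeated. In Phase 2 the LUX-Dx record can be resampled at will, and the classifications exist already, since under Appendix A 11.2 "Atrial arrhythmia episodes (asymptomatic and symptomatic) captured by the LUX-Dx ICM will be analyzed by BeatLogic Core Lab Adjudicator Tool". A pre-specified redraw would also carry more weight than one done after a borderline result, which is where post hoc checks persuade least. The tipping point in 8.3.3.6 measures a margin and does not show how the estimate moves between seeds. The continuous-monitoring endpoints in 3.5.2 avoid the draw but measure a different quantity.

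All of that is true. Section 8.3.3 contains no such analysis, and a redraw table would be harmless. But the argument supports an optional extra and does not show a defect. The chance timing of a routine transmission is a feature of the Phase 1 monitoring that Phase 2 sets out to imitate, and fixing the seed by rule takes the choice of draw away from the analyst. A redraw would leave the primary test, sample size and error rate unchanged. The plan would also still need a rule for reading a result such as 70% of draws passing. Anyone who needs the answer can compute it from data the sponsor undertakes to provide, and the separate SAP may already include it.

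**Conclusion.** The concern does not call for a change. The protocol does rest the simulated event-monitor component on one seeded draw and pre-specifies no variation of it. Followed as written, though, the analysis is valid: the draw is unbiased, the type I error holds, and the draw noise sits inside the planned interval. On assumed burden inputs the seed moves the success rate by an SD of about 0.2 to 1.7 points. It could alter the verdict only when the rate lies within roughly 1 to 2 points of 46.5%, a little wider under the harshest inputs, and it is immaterial at 55%.

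These sizes rest on invented burden, episode length and share of window-dependent subjects, on no censoring, and on hits being independent between subjects. They leave out the stored-S-ECG requirement and the device's detection-duration settings. The conclusion that the test is sound depends on none of the burden figures. What remains is a gap an analyst can fill sensibly if the result proves close.
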